## 9.3 POPULATIONS FOR ANALYSES

For the primary endpoint comparison, an intention-to-treat analysis will be used, including all available data on randomized participants. It is expected that up to 20% of randomized participants may discontinue from the study prior to the end point. These participants will be included in the primary analysis and data from the monthly outcome ascertainment up until the last available time point will be used. As preparation for the follow-up period modification, events to date were evaluated at one site (Einstein) and were found to be more frequent than initial estimates. This informed the request for reduction in the follow-up period.

The characteristics of those who do not complete all study activities will be compared to those with complete follow-up to examine for potential biases introduced by differential follow-up among the two groups. These will be considered ancillary analyses.

Secondary analyses will examine additionally an as-treated population. This will group any intervention patient who did not participate in more than 20 minutes total of the intervention during the three-month period to be classified as the usual care group.

## 9.4 STATISTICAL ANALYSES

### 9.4.1 GENERAL APPROACH

Descriptive statistics will be used to provide for each variable: number of observations, mean, standard deviation, median, minimum and maximum for continuous variables; frequencies and proportions for categorical variables. Results will be reported in accordance with the extended CONSORT guidelines for pragmatic clinical trials using two-sided statistical tests and confidences intervals. For all analyses, the overall level of significance will be set at 0.05. All analyses will be adjusted for site. Adjustment variables will be pre-specified in the following sections. All analyses will be performed using SAS v9.4 (SAS Institute, Cary, NC), STATA (College Station, Tx), or R (currently 3.6.1; <https://cran.r-project.org/>).

Analyses of qualitative data will include content analysis, novel code generations as applicable, interpretation and descriptive reporting.

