**Summary of Changes from Previous Version:**  
*See section 10.4 for detailed description*

Affected Section(s)	Summary of Revisions Made	Rationale	Date of Revision
Throughout Protocol	Remote consent procedure (telephone, email, or mail)	Re-opening of study after COVID crisis to accommodate social distancing	6/9/20
5.1	Inclusion Criteria (10) to include "or Spanish – Bronx, NY site)	Grammatical error	6/10/20
9.4.2	Analysis of the Primary Endpoints – ED Visit and Hospitalization Count language revision	Biostats review deemed revisions	6/10/20
9.4.3	Analysis of Secondary Endpoints & Feasibility Outcomes language revisions	Biostats review deemed revisions	6/10/20
9.4.5	Baseline Descriptive Statistics language revision	Biostats review deemed revisions	6/10/20
Throughout Protocol	Primary endpoint follow-up period from 18 months to 9 months (12 months observational)	Timeline revision due to COVID pandemic	4/30/21
6.1	Assignment of 3 mentees per mentor revised to 4 mentees	Mentee assignment revisions to meet timeline goals	4/30/21
7.2	T2 surveys administered at time of discontinuation	Established assigned discontinuation surveys	4/30/21

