### 1.2 SCHEMA

**Figure 1. Mentors N~20**

**Figure 2. Patient Participants N=200 [All sites; Estimated enrollment AECOM=140; VUMC=60]**

At the final study visit, all mentors and those randomized to the peer mentoring intervention will complete program evaluation interviews and surveys to gain feedback on the intervention.

Due to impact of the covid pandemic, the study DSMB recommended prioritizing enrollment and reduction of follow-up observational time. The recommendation is to limit total observation time to 12-months for intervention and control participants. Participants currently enrolled and who have passed the 12-month point will execute their T2 visit as soon as possible and truncate observation (13-18 months). For those whose observation time is less than 12-months, or any new enrolled participants, the T2 assessment will be moved to the 12-month time point. Mentors, may complete T2 at 18-months (Einstein site), or may complete T2 visit at 12-months if all other mentor activities have been completed at the site. Medical record monthly review will only occur for the observation period and will also be truncated at the time of the T2 visit. This alteration of the study design was approved by the DSMB and also the NIH program officer.

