#### 5 STUDY POPULATION

Subjects for this study will be selected from a population of patients with ESKD on maintenance hemodialysis who receive treatment in one of affiliated dialysis facilities in the Bronx and Nashville. The study population is comprised of dialysis patient Mentors and Mentees or Usual Care.

The study population will consist of approximately 17 mentors (7 in Nashville and 10 in the Bronx) who will be trained by the study team using the developed mentor training modules (Figure 3). We will make it clear during the consent process that not all mentors may participate in the intervention phase. After mentor training, each mentor will be assigned to 1-4 intervention mentees for 3-month periods. Patient participants will be recruited to try to achieve balance in the 1:1 allocation to intervention or usual care groups during study periods. There may remain differences in the counts in each group during each period depending upon randomization allocation.

Figure 3. Schema summary of mentor and patient group participants.

At some dialysis facilities a HIPAA waiver form may be required to be signed by a potential participant prior to screening. This will depend upon individual facility requirements. A verbal consent may also be required by site-specific IRB processes or local regulations to proceed with screening.

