## 6.3 MEASURES TO MINIMIZE BIAS: RANDOMIZATION AND BLINDING

We will randomize enrolled patient participants after completion of informed consent and the baseline visit utilizing a random number generator. As each subject is enrolled we will select envelopes with the random assignment to either the intervention or the usual care control group (1:1). The randomization will occur in blocks of between 28 to 42 depending upon the number of mentor and planned assigned mentees at the site. The goal is to have approximately equal total number of enrolled participants within each ~3-month intervention period. There may be staggering of the window and timeline depending upon enrollment pacing.

The mentee assignments will be blinded to usual care nephrologist and dialysis staff, but not to study subjects and mentors, because of the nature of intervention. The research team additionally will not be blinded to group assignment. While this may be preferred, it is not feasible in this pragmatic trial.

Enrolled participants will be encouraged to complete visit surveys on their own, to limit interactions with study staff in the process of data collection.

Trial randomization codes will be stored in a single file maintained by the data coordinating center. They will be shared with the research team as described above for patient participant assignment. Should accidental unblinding occur prior to completion of a baseline visit for a participant, the PI will be notified and this will be documented as a protocol deviation.

No change in study activities will occur in the event that it is identified that a usual care provider is unblinded to study assignment of their patient.

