#### 9.4.2 ANALYSIS OF THE PRIMARY ENDPOINT(S)

##### ED Visit and Hospitalization Count

Each month all enrolled patients will be evaluated for ED visit or hospitalization encounters by both self-report and medical record review. The events will be tabulated each month up to an 18-month period of follow-up. The rates of the composite event will be determined as event per patient-month and compared between the intervention and usual care group using Poisson regression with two random intercepts. In the regression model, the composite counts of ED visits and hospitalization during up to 18-months follow-up is the outcome variable and the intervention assignment of the mentees is the primary binary predictor. The log of follow-up time will be included as offset. The random intercepts will account for the correlation between mentees who share a common mentor as well as the correlation between mentees who are from a common dialysis facility (out of seven facilities). As a randomized controlled trial, we do not anticipate the need for covariate adjustment. However, if evaluation of patient characteristics by group identifies a failure of randomization and imbalance in key characteristics as an example including age, gender, comorbidity, race, or dialysis vintage they will be considered as adjustment variables in the analysis. We will control for type 1 error at 0.05. An exploratory analysis will consider the comparison between the groups but at 3-months of observation after the conclusion of the intervention delivery.

We will perform residual analysis for the mixed effects models. For mixed effects models, we will examine marginal residuals to check linearity and within-subjects covariance matrix and conditional residuals to check outliers as well as normality and homoscedasticity of the residual errors. In case Pearson residual analyses indicate overdispersion in the Poisson mixed effects model, we will perform quasi-Poisson model. We will use robust sandwich estimator in the presence of misspecification of the covariance matrix (i.e. random effects structure).

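### The primary model leaves out the randomisation blocks, which follow roughly 3-month periods on both sides of the COVID closure; under the quasi-Poisson fallback this costs a modest amount of power

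*Combined protocol and SAP*

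**What the plan says.** **Randomisation.** Section 6.3: "The randomization will occur in blocks of between 28 to 42 depending upon the number of mentor and planned assigned mentees at the site". The next sentence ties this to time: "The goal is to have approximately equal total number of enrolled participants within each ~3-month intervention period". The reference to mentors and mentees at the site suggests separate blocks per site, but this is not stated outright. Section 5 accepts imperfect balance: "There may remain differences in the counts in each group during each period depending upon randomization allocation".

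**Calendar time.** The summary of changes gives the reason for the June 2020 consent revision as "Re-opening of study after COVID crisis to accommodate social distancing". Section 1.2, revised on 30 April 2021, still provides for new patients: "For those whose observation time is less than 12-months, or any new enrolled participants, the T2 assessment will be moved to the 12-month time point". It also provides for participants already past 12 months, who must have started by the end of April 2020, before the re-opening revision. Enrolment therefore lies on both sides of the closure.

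**Analysis.** Section 9.4.1: "All analyses will be adjusted for site", followed by "Adjustment variables will be pre-specified in the following sections". The primary model in 9.4.2 is a Poisson regression with random intercepts for mentor and facility and log follow-up time as offset. On covariates it says "As a randomized controlled trial, we do not anticipate the need for covariate adjustment", and allows adjustment only if patient characteristics turn out imbalanced; its examples do not include block or period. If Pearson residuals show overdispersion, a quasi-Poisson model is to be used.

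**The concern.** The block is the group within which the trial randomises, and here it also marks calendar time. Emergency department and hospital use may well have differed between patients enrolled before the closure and those enrolled after it. Site and facility describe places, and the offset corrects for length of observation, not for a different event rate. Site is the only unconditional fixed adjustment, so no term in the primary model takes up a difference between blocks.

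Two consequences are possible. First, when dispersion is estimated from the data, between-block variation counts as residual noise and widens the standard error, although balanced allocation within blocks has already removed it from the arm comparison. Second, if blocks are cut short or patients drop out, arms can differ by chance in their mix of periods. A period term added after seeing the data would be open to challenge, so the choice should be made beforehand.

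**Working it through.** **1. The plan's power figure (Section 9.2).** Inputs: 0.27 events per patient-month, a 20% reduction to 0.216, 73 per arm, two-sided 0.05. At 18 months, expected events are 73 × 18 × 0.27 = 354.8 and 73 × 18 × 0.216 = 283.8. The SE of the log rate ratio is √(1/354.8 + 1/283.8) = 0.0796. Power = Φ(0.2231/0.0796 − 1.96) = 0.80, so the stated figure reproduces. At 12 months the same formula gives 0.63 with 73 per arm and 0.76 with 100. That is a separate matter, but it shows there is little power to spare.

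**2. Number of blocks.** 200/42 = 4.8 and 200/28 = 7.1, so about 5 to 7. As a fixed factor that is about 4 to 6 degrees of freedom.

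**3. How a period difference reaches the standard error.** Take equal early and late halves with later-to-earlier rate ratio r. The squared coefficient of variation is [(1 − r)/(1 + r)]²: 0.0204 at r = 0.75 and 0.1111 at r = 0.5. The mean count over 12 months, both arms, is 12 × (0.27 + 0.216)/2 = 2.916. Dispersion from period alone is therefore 1 + 2.916 × 0.0204 = 1.06, or 1 + 2.916 × 0.1111 = 1.32. Plain Poisson fixes dispersion at 1 and ignores this; quasi-Poisson multiplies the SE by its square root.

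**4. Simulated power under quasi-Poisson.** 200 patients (140/60 by site), 7 site-by-period blocks, 12 months, true rate ratio 0.8, 3000 trials per row. The values of r and the between-patient variance are assumed, because the documents give neither. Truncated means blocks of 42 stopped at 25 to 30.

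| Blocks | Patient variance | r | Site only | With block/period |
|---|---|---|---|---|
| Complete | 0 | 0.75 | 0.744 | 0.755 |
| Complete | 0 | 0.5 | 0.686 | 0.757 |
| Complete | 0.5 | 1 | 0.406 | 0.411 |
| Complete | 0.5 | 0.75 | 0.404 | 0.417 |
| Complete | 0.5 | 0.5 | 0.342 | 0.416 |
| Truncated | 0 | 0.75 | 0.757 | 0.764 |
| Truncated | 0 | 0.5 | 0.688 | 0.758 |
| Truncated | 0.5 | 0.75 | 0.397 | 0.415 |
| Truncated | 0.5 | 0.5 | 0.343 | 0.393 |

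With complete blocks and no patient variance, type I error is 0.040 (site only) against 0.043 (with block) at r = 0.75, and 0.019 against 0.046 at r = 0.5. With variance 0.5 it is 0.050 against 0.056, and 0.039 against 0.059. The slight excess with the block term is not caused by period differences: at r = 1 the figures are 0.057 and 0.059.

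**5. Cross-check with a different set-up.** Six blocks with between-block log-rate SD 0.2 or 0.4, patient variance 0.5, 12 months, 250 trials per setting. Mean SE, site only against block: 0.1286 against 0.1251 (SD 0.2) and 0.1371 against 0.1256 (SD 0.4). Φ(0.2231/SE − 1.96) gives 41.1% against 43.0%, and 37.0% against 42.7%. In closed form, with 0.27 × 12 = 3.24, the SE ratio is √{[1 + 3.24(0.5 + SD²)]/[1 + 3.24 × 0.5]}: √(2.7496/2.62) = 1.024 and √(3.1384/2.62) = 1.094. The simulated ratios are 1.028 and 1.092.

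**6. Plain Poisson, no patient variance.** With complete blocks the block term changes nothing: power is 0.766 with and without it at r = 0.75, and 0.769 with and without it at r = 0.5. With patient variance 0.5, however, plain Poisson has type I error of about 0.24, so the fallback would be needed.

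**7. Arm-by-period imbalance.** Zero with complete blocks. With truncated blocks, the arm share differs between early and late periods by about 0.03 on average. At r = 0.5 without patient variance, the SD of the estimate under the null is 0.083 against 0.080 with the block, and plain Poisson type I error is 0.061 against 0.054.

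Neither simulation includes mentor or facility intercepts, and the robust sandwich option in 9.4.2 was not simulated.

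**The case against.** The strongest reply is that the planned primary model is plain Poisson and that, with complete 1:1 blocks, adding the block leaves it unchanged. The widening of the standard error is therefore conditional on the fallback. This stands as a limit on the claim. It does not remove it: Section 5.1 admits patients on any one of eight diverse risk criteria, so overdispersion is likely, and 9.4.2 plans for it.

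A second reply is that large period differences are assumed, and that patients enrolled before the closure were themselves followed into the pandemic, which dilutes differences between blocks. This also stands. With equal early and late halves, block SD 0.4 means a later rate exp(−0.8) = 45% of the earlier one over the whole follow-up. Halving the rate for 6 of 12 months in half the blocks gives an average ratio of 0.75, an SD of about |log 0.75|/2 = 0.14. The moderate figures are the safer guide. Section 9.3 says events at one site exceeded the initial estimates, but nothing about differences between periods.

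Third, Section 6.3 allows staggered windows, so a block need not coincide with one calendar period and might itself span the closure. This is a reason to use the block as allocated rather than a constructed period.

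**Conclusion.** The gap is real and worth closing, but its cost is modest. If the quasi-Poisson fallback is used, omitting the block makes the test conservative. The loss is about 1 to 2 power points at a rate ratio of 0.75 or block SD 0.2, and about 6 to 7 at a ratio of 0.5 or SD 0.4 (5 in one truncated-block setting). These sizes rest on assumed period differences and patient variance, and on models without the mentor and facility intercepts.

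A reader might infer more than the documents support:

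- **That the model adjusts for site and nothing else.** Section 9.4.2 also has mentor and facility intercepts, an offset and contingent covariates. None of them is a block or period term.
- **That period differences bias the treatment effect.** Allocation is 1:1 within blocks. Imbalance arises only from incomplete blocks or drop-out, is a matter of chance, and is small.
- **That unequal follow-up is left unhandled.** Observation of 12 against 13 to 18 months follows enrolment date, and the offset deals with its length.
- **That the secondary models need the same change.** In 9.4.3 the monthly endpoints are compared by slope with a subject intercept, which already largely absorbs level differences between blocks. No gain has been shown.

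**What to change.** In Sections 9.4.1 and 9.4.2, state that the primary model will include the randomisation block, exactly as used in the allocation list, as a fixed categorical term, and that the term is kept in the quasi-Poisson fallback. If blocks are site-specific, it replaces the separate site term; if not, it is added to site. Section 6.3 should say which applies. The secondary slope models can stay as they are on this ground.

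The cost is a sentence in the plan and about 4 to 6 degrees of freedom out of 200 patients. Section 6.3 says the coordinating center keeps the randomisation codes, so no new data should be needed. If blocks do not differ, the standard error changes by under 1%. The term captures only the part of any calendar-time effect that follows the block of enrolment, because follow-up of earlier blocks can run into the pandemic too.

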#### 9.4.2 ANALYSIS OF THE PRIMARY ENDPOINT(S)

##### ED Visit and Hospitalization Count

Each month all enrolled patients will be evaluated for ED visit or hospitalization encounters by both self-report and medical record review. The events will be tabulated each month up to an 18-month period of follow-up. The rates of the composite event will be determined as event per patient-month and compared between the intervention and usual care group using Poisson regression with two random intercepts. In the regression model, the composite counts of ED visits and hospitalization during up to 18-months follow-up is the outcome variable and the intervention assignment of the mentees is the primary binary predictor. The log of follow-up time will be included as offset. The random intercepts will account for the correlation between mentees who share a common mentor as well as the correlation between mentees who are from a common dialysis facility (out of seven facilities). As a randomized controlled trial, we do not anticipate the need for covariate adjustment. However, if evaluation of patient characteristics by group identifies a failure of randomization and imbalance in key characteristics as an example including age, gender, comorbidity, race, or dialysis vintage they will be considered as adjustment variables in the analysis. We will control for type 1 error at 0.05. An exploratory analysis will consider the comparison between the groups but at 3-months of observation after the conclusion of the intervention delivery.

We will perform residual analysis for the mixed effects models. For mixed effects models, we will examine marginal residuals to check linearity and within-subjects covariance matrix and conditional residuals to check outliers as well as normality and homoscedasticity of the residual errors. In case Pearson residual analyses indicate overdispersion in the Poisson mixed effects model, we will perform quasi-Poisson model. We will use robust sandwich estimator in the presence of misspecification of the covariance matrix (i.e. random effects structure).

All data analyses will be preceded by extensive data checking and verification to identify and resolve the reasons for missing values, inconsistencies, and out-of-range values. Although, we anticipate less than 15% missing data, we will carefully examine whether missingness is completely at random (MCAR), at random (MAR) or informative (MNAR). Models proposed for analysis can handle incomplete data (i.e. entire subject is not deleted if missing data at one time point), but do require at least that missingness be at random. Modelling will consider using multiple imputation techniques of covariates to reduce potential biases.

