## 2.2 BACKGROUND

### 2.2.1. Excessive hospitalization rates in patients treated with hemodialysis

There are over 400,000 ESKD patients in the United States and they constitute one of the most clinically complex and expensive patient groups. Patients treated with hemodialysis comprise 1% of the Medicare population but account for close to 9% of the total expenditures. Hospitalizations drive up to 40% of the cost for ESKD care. Patients receiving hemodialysis are hospitalized, on average, 2 times per year and over 35% of these patients are re-hospitalized within 30 days of discharge. During hospitalizations, patients' nutritional status and mobility deteriorate, and the risk for infectious complications increases, all of which add to short-term morbidity and mortality.

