### 2.2.2. Hospitalizations are avoidable in patients treated with hemodialysis

Cardiovascular disease is the most common cause of hospitalizations in patients on hemodialysis, followed by infections and vascular access complications. In the U.S., the rate of hospitalization for fluid overload is 40 per 100 person year with a risk of 30-day re-hospitalization of 38%. Fluid overload presenting as heart failure is the most common reason for ED visits in the U.S. and Canada. Chronic fluid overload is common in patients treated with hemodialysis, is related to EDW achievement for each treatment, dialysis adherence and IDWG, and contributes to excessive and avoidable hospital resource utilization. In a study examining the types of US claims used for fluid related ESKD hospitalizations, heart failure was the primary diagnosis in 83% of episodes, average cost was \$6,372 per episode, and importantly total costs were more than \$266 million per year. Patients on hemodialysis rarely demonstrate understanding of the metrics of EDW and IDWG that are important for patients' ability to set goals, problem solve and understand their symptoms. Complications related to low dialysis adherence contribute to avoidable hospitalizations in other ways and include infection risk, uremia related malnutrition and cognitive decline. Dialysis adherence and recognition of vascular access malfunction are important to prevent low dialysis clearance and malnutrition. Patients are given monthly reports of dialysis parameters but they infrequently recognize its relation to uremia, access dysfunction, associated symptoms, and to outcomes. Poor patient self-management is associated with: 1) low dialysis adherence, 2) lack of self-examination of access and 3) dietary non-adherence to IDWG limits leading to fluid overload, and malnutrition. These behaviors, in turn, lead to chronic and maladaptive clinical changes such as ventricular dysfunction and vascular calcification which increase the risk of hospitalizations in part attributed to self-referral to the ED because of poor understanding of and communication about fluid related symptoms by the patient to their clinician.

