### Patient Participants [Intervention or Usual Care]

Patient participants must meet all of the following inclusion criteria:

1. Provision of signed and dated informed consent form
2. Stated willingness to comply with all study procedures, including randomization, and availability for the duration of the study
3. Males and females; Age > 21 years
4. Dialysis treatment at one of the participating dialysis units
5. One of the following criteria:

- a. Diagnosis of ESKD and treatment with in-center hemodialysis for less than 90 days
- b. One or more hospitalizations in the prior month
- c. One or more ED visits in the prior month
- d. More than 1 unexcused missed dialysis treatments in the prior month
- e. 2 or more shortened (more than 10 minutes) dialysis treatments in the prior month
- f. Use of a catheter for dialysis access
- g. An average of more than 4% IDWG in any week during the prior month
- h. Serum albumin less than 3.5 mg/dL in the prior month
6. Fluent in English (or Spanish – Bronx, NY site)

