#### **Usual Care control group**

The usual care control group will be under the clinical care of the usual providers. The study will provide two kidney educational documents to the patient: 1. Kidney School: Follow Your Treatment Plan; and 2. National Kidney Foundation: Hemodialysis Access. They will also receive study-specific educational materials that are also provided to mentors. This includes: Mentor Training Manual Appendix documents 1 (EDW information), 2 (Skills checklist for fluid), 4 (Uremia information), 5 (What to do for uremia), and 6 (Information card).

---

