**Table 4. Scientific Questions to be Addressed with the Trial**

Scientific question	Outcome(s)	Analysis
1. Does phone peer support improve outcomes at 18-months (*12 to 18-months)?	
 
Primary: composite endpoint count of ED visit and hospitalization events
 
Secondary: Various as listed above
 
	Poisson regression with two random intercepts. Random intercepts account for clusters by (1) mentor; (2) dialysis unit  See Section 9.4.2 (Primary); 9.4.3 (Secondary)
2. Is a peer mentor training program feasible?	
 
Attendance records
 
Pre- and Post-knowledge test scores
 
Satisfaction with training
 
Summative assessment
 
	Paired t-tests  Descriptive summaries and content analysis of qualitative data
3. Is a peer mentor training program accepted by patient receiving hemodialysis	
 
Satisfaction with intervention
 
Communication rating of mentors
 
	Descriptive  Content analysis of qualitative data

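### Section 9.4.2 leaves open how usual-care patients enter the mentor term, and the cut-off and form of the overdispersion fallback; if event rates vary between patients, the size and power of the primary test depend on these choices.

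*Combined protocol and SAP*

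**What the plan says.** Section 9.4.2 analyses the composite count of ED visits and hospitalisations by Poisson regression with two random intercepts and a log follow-up offset. Table 4 (Section 9.1) describes them: "Random intercepts account for clusters by (1) mentor; (2) dialysis unit". Section 9.4.2 adds: "The random intercepts will account for the correlation between mentees who share a common mentor". Neither place includes a patient-level variance term.

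Section 6.1.1 describes the other arm: "The usual care control group will be under the clinical care of the usual providers". Those patients have no mentor, and no section gives them a level of the mentor factor.

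Two safeguards follow in Section 9.4.2. The first is "In case Pearson residual analyses indicate overdispersion in the Poisson mixed effects model, we will perform quasi-Poisson model". The second is "We will use robust sandwich estimator in the presence of misspecification of the covariance matrix". The diagnostic for the first is therefore named. Missing are the statistic and cut-off, whether the quasi-Poisson model keeps the two intercepts, and the test and cluster unit for the sandwich estimator. The section sets type I error at 0.05 and adjusts for baseline characteristics only if an imbalance is seen.

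**The concern.** With one count per patient, a Poisson model takes the variance of the count to equal its mean, given mentor and facility. If patients differ in their underlying event rate, the variance is larger. The mentor term can then absorb part of the excess, and how it does so depends on the coding of controls. Three codings fit the text:

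- **Mentee-only:** the effect is zero for usual care.
- **Shared:** all controls form one level.
- **Singletons:** each control is its own level.

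The wording favours the first but does not settle it. Sections 9.4.2 and 9.4.3 also use the word mentees for patients in both arms, including control mentees.

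Uneven risk is plausible in this population. Eligibility (Section 5.1) needs any one of eight different criteria, for example "One or more hospitalizations in the prior month". Section 2.2.1 describes patients as "hospitalized, on average, 2 times per year and over 35% of these patients are re-hospitalized within 30 days of discharge".

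At stake are the size and power of the primary test. Section 6.3 says that the research team is not blinded to group, so these choices should not be left until data by arm are visible.

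**Working it through.** **1. The plan's own power figure.** Section 9.2 gives 0.27 events per month, a 20% reduction, 73 per group and type I error 0.05; Section 9.4.1 gives two-sided tests. For follow-up T months, μ0 = 0.27T and μ1 = 0.8μ0, and power = Φ(|ln 0.8| / √[(1/μ0 + 1/μ1)/n] − 1.96).

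- T = 18: μ0 = 4.86, μ1 = 3.888, SE = √(0.46296/73) = 0.0796, 0.2231/0.0796 = 2.80, power 80.0%. This reproduces the stated figure.
- T = 12, same n: SE = √(0.69444/73) = 0.0975, ratio 2.29, power 63%.

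The calculation contains no overdispersion and no clustering.

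**2. Effect of patient variance k (assumed; not in the documents).** With gamma-distributed patient rates the variance of the log rate ratio becomes (1/μ0 + 1/μ1 + 2k)/n. At T = 18, n = 73, k = 0.5: SE = √(1.46296/73) = 0.1416, ratio 1.58, power 35%. This loss comes from heterogeneity and not from the model wording. The variance-to-mean ratio in controls is 1 + kμ0 = 1 + 0.5 × 4.86 = 3.43.

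**3. Is k > 0 plausible?** At a common rate of 2 admissions a year, the chance of re-admission within 30 days of a discharge is 1 − exp(−2 × 30/365) = 15%. Counted per hospitalised patient over a year it is 27%. With k = 0.5 these are 21% and 32%; with k = 1, 26% and 36%. The figure of over 35% in Section 2.2.1 exceeds the common-rate value on both readings, less clearly on the second. The 38% in Section 2.2.2 follows fluid-overload admissions, a selected group. Short-term clustering after discharge may explain part of both, so k is not identified.

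**4. Simulation.** Two set-ups were used, both with 17 mentors (Section 5), 7 facilities (Section 9.4.2), gamma patient rates and Laplace-fitted mixed models.

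- Set-up 1: 200 patients, 12 months, 20% discontinuing at uniform times, site adjusted, facility SD 0.15 (assumed), 1000 trials per scenario.
- Set-up 2: 73 per arm, 18 months, no true mentor or facility effect, no site term, 600 trials per scenario.

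Before any fallback:

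| Quantity | Set-up | k = 0 | 0.25 | 0.5 | 1 |
|---|---|---|---|---|---|
| Mentee-only, type I error | 1 | 4% | 11% | 12% | 16% |
| | 2 | 6% | 10% | 15% | 22% |
| Singletons, mean rate ratio under the null | 1 | 1.00 | 1.03 | 1.10 | 1.27 |
| | 2 | 1.00 | 1.05 | 1.11 | 1.26 |
| Shared, model SE / empirical SD | 1 | 1.1 | 1.4 | 1.9 | 2.4 |

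Power at true rate ratio 0.80, k = 0.5, with the fallback:

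| Fallback | Set-up | Mentee-only | Shared | Singletons |
|---|---|---|---|---|
| Intercepts dropped | 1 | 39% | 39% | 14% |
| | 2 | 34–35% | 34% | 18 / 7 / 6% |
| Intercepts kept | 1 | 35% | 12% | 7% |
| | 2 | 28% | 5% | 4% |

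The trigger is an assumption. Set-up 1 used a 5% Pearson chi-square test. Set-up 2, with intercepts dropped, used dispersion above 1.2, 1.5 and 2.0 (the three singleton figures, in that order); with intercepts kept, the SE was scaled in every trial.

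At k = 0, set-up 1 gives 69–72% for all codings and both fallbacks.

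**5. The trigger.** At k = 0.5 and rate ratio 0.80, mentee-only and shared codings fire in 97% or more of trials at every cut-off in set-up 2, so the cut-off hardly matters there. Singletons absorb the control-arm overdispersion: firing falls to 50%, 7% and 0% at cut-offs 1.2, 1.5 and 2.0 in set-up 2, and is 29% with the Pearson test in set-up 1. The masking is partial and shrinks as k grows (78% firing at k = 1 in set-up 1).

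**6. Alternatives, set-up 1 inputs.** A negative binomial mixed model with a mentee-only mentor effect has type I error 4 / 6 / 6 / 5% and power 71 / 49 / 39 / 24% at k = 0 / 0.25 / 0.5 / 1. A Poisson model without intercepts and with a sandwich SE clustered on mentor (3000 trials) has 40% power at k = 0.5. With an assumed mentor SD of 0.2, type I error is 5.3 / 5.6 / 5.9 / 5.2% for the negative binomial and 6.1 / 5.7 / 6.5 / 6.2% for the clustered sandwich.

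**7. Baseline count as covariate.** Added to the negative binomial at k = 0.5, look-back windows of 1 / 3 / 6 / 12 months give 42 / 44 / 49 / 54% power against 39% without, a gain of 3 to 15 points. There is no gain at k = 0. These figures assume the same patient rate before and after baseline. A run with selection on a prior-month event gave 38% to 44% at k = 0.5 and 30% to 37% at k = 1, with no loss at k = 0.

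**The case against.** The strongest defence is that the natural reading already works. A term for patients who share a mentor has no meaning for patients without one, and the fallback is called a quasi-Poisson model, not a mixed one, which suggests that the intercepts go. On that reading set-up 1 gives type I error of 4–7% and the same 39% power at variance 0.5 as the negative binomial. The sandwich estimator, once given a cluster unit, does about as well. All of this stands, and it limits the point.

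A reader might infer more than the documents support:

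- **That the plan has 4–7% power.** This needs singleton coding, retained intercepts and an assumed variance of 0.5 together. The text requires none of them.
- **That the fallback has no trigger.** Section 9.4.2 names Pearson residuals indicating overdispersion. Only the statistic and cut-off are missing.
- **That the model is anti-conservative however controls are coded.** Shared coding inflates the SE; in set-up 2 its type I error was 4% or less for variances of 0.25 and above. It costs power, not size.
- **That a negative binomial model would add power.** It does not.

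What the defence does not remove is that the favourable reading has to be inferred on three points. A sandwich SE also cannot repair the shifted estimate under singleton coding.

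**Conclusion.** The point holds as an incomplete specification of the primary test. If patient rates vary (assumed variance 0.25 to 1), the unscaled mentee-only model has type I error of about 10–22%. Singleton coding moves the rate ratio towards no benefit and partly hides the overdispersion that should trigger the fallback. Shared coding inflates the SE. On the most natural reading the plan is close to valid, with 34–39% power at variance 0.5. The fall to that level from about 70% (set-up 1, variance 0) comes from the assumed heterogeneity; only the spread below it comes from the unstated choices. With no patient variance they barely matter.

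The sizes rest on gamma patient rates, 17 mentors and the assumed triggers. Monte Carlo error in set-up 1 is about 1.4 points at 5% and 3 points at 40%. Wald tests from other software may differ somewhat. This should be fixed before any analysis by arm.

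**What to change.** Replace the Poisson model and residual-triggered switch with a primary analysis that allows overdispersion from the start, with log follow-up offset, site (Section 9.4.1) and facility. Either of these would serve:

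1. A negative binomial mixed model with a facility intercept and a mentor effect in the intervention arm only, zero for usual care. Use the first assigned mentor, because Section 5.5 allows re-matching.
2. A Poisson or quasi-Poisson model without random intercepts, with a sandwich SE clustered on mentor and each control as its own cluster.

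They perform similarly and neither adds power; the gain is a defined, size-controlled test. If the present structure is kept, the minimum is to state that the mentor effect applies to mentees only, that the fallback drops both intercepts, the dispersion cut-off, and the sandwich cluster unit. Without that clustering, mentor correlation is unmodelled once the fallback is used.

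Separately, replace the imbalance-triggered adjustment in Section 9.4.2 with a pre-specified baseline ED and hospitalisation count, already collected under Section 8.1, and state its look-back window. The gain may be smaller than in step 7, because patients are selected on recent events and some are new to dialysis (Section 5.1).

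The cost is SAP wording and slightly more modelling work, with no new data and no burden on patients.
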